11.2 Structure And Content Of Treatment Sessions

Resting MT will be determined prior to initial treatment using the Parameter Estimation by Sequential Testing (PEST) algorithm. A revised MT will be determined in the following clinical scenarios:

1. If UDS becomes positive for methamphetamine or cocaine after previously being negative.
2. If participant reports increased methamphetamine or cocaine use since last treatment.
3. If participant has had 10 treatments without repeat motor threshold determination.
4. Study Medical Clinician determines, based on their clinical judgement, seizure threshold has decreased for any other reason.

Whenever MT is retested, treatment intensity for the following rTMS sessions will be based on the revised MT.

Topical anesthetic (e.g., EMLA, Lidocaine or Lidocaine/Prilocaine) may be applied prior to rTMS/sham to help reduce scalp discomfort.

Prior to each treatment stimulation onset, a set of cocaine or methamphetamine-related cues will be presented to the participant. Immediately after the offset of the cue presentation (while memory is reactivated) active or sham rTMS stimulation will be administered.

Each treatment session will consist of 75 rTMS trains of 10 Hz for 4 seconds with inter-train interval (ITI) of 11 seconds (a total of 3000 stimuli per session) over the left DLPFC (19 minutes). These parameters are consistent with those recommended in a recent consensus statement for rTMS treatment for Major Depressive Disorder (McClintock et al., 2018).

The rTMS coil will be placed over the DLFPC using the Beam F3 method. Participants in the control group will receive sham treatment in a similar manner. Administration of active versus sham rTMS will be determined by the computer controlling the coil; randomization status will have been entered into files used by the device computer during DSC randomization. Treatment assignment will not be revealed to the participants or study personnel (double-blind). To improve treatment tolerability, a ramp-up will be used where the stimulation intensity is gradually increased

during the treatment session. Participants will be expected to ramp to full intensity by the tenth rTMS/placebo session; however, participants will not be excluded if they are unable to tolerate the full treatment dose. Rather, ramp up will be attempted every 5 sessions and dose will be documented.

11.3 Sham rTMS

Adequate sham stimulation protocols are a critical factor in clinical trials to ensure that effects can be ascribed specifically to rTMS. Since rTMS generates sensory perceptions, such as clicking sounds, and muscle contractions (Conde et al., 2019), sham strategies aim to mimic the sight, sound, and feel of real stimulation, while attempting to avoid any direct neuronal effects on the central nervous system. The delivery of active versus sham intervention will be controlled by a dual active/sham coil. Administration of active versus sham rTMS will be determined by the computer controlling the coil; randomization status will have been entered into files used by the computer during DSC randomization. With this procedure, rTMS Operators and other research staff will be kept blind to participants' condition assignments. In the sham condition, participants and staff will hear identical sound as active treatment, but the magnetic field will be delivered in the opposite direction (away from the brain). Additionally all participants will be equipped with small electrodes on the scalp adjacent to the magnetic coil. In the sham condition, the device will discharge a very mild electrical stimulation through those electrodes to mimic the tactile sensation of the magnetic field. This stimulation can cause muscle twitching and tactile sensation, but unlike magnetic stimulation does not penetrate the brain. For participants with prior rTMS exposure, the lack of tactile sensation from the magnetic field in the sham condition could lead to unblinding and hence prior exposure is exclusionary for study participation. Sham rTMS approaches require further development but are sufficient in clinical settings in which patients are generally naïve to rTMS as will be the case in this study (Duecker & Sack, 2015; Y. Levkovitz et al., 2015; C.E. Sheffer et al., 2013).

11.4 Scheduling

Every effort will be made to be flexible in scheduling rTMS visits, including Saturday and after-hours sessions (site resources permitting) and scheduling 2 rTMS sessions on 1 day (site resources permitting). Participants will receive study intervention over 8 weeks in order to complete up to 30 rTMS sessions. End of treatment assessment will be scheduled within 1 week after the last treatment session. Follow-up assessments will be scheduled at weeks 12 and 16 post-randomization.

The interval between rTMS sessions will vary over the course of the study and for each participant depending on individual scheduling needs, with the primary objective being that each participant receives an adequate dose of treatment (at least 20 sessions) with flexibility in the timing of rTMS delivery to minimize study drop-out. The target minimum number of treatments is 20 treatments over 8 weeks, with an ideal number of 30 treatments. No more than 5 treatments are permitted in a study week. Initially, participants are encouraged to complete 5 treatments per week and hence complete 20 treatments within 4 weeks. Weeks 5-8 are planned as a taper, but can be used to make up missed visits. Participants who miss a treatment, may also receive up to 2 treatments on a given day. Multiple treatments on a given day should be spaced at least 1 hour apart, from

the time the first treatment session ended. Therefore, some participants may be able to receive 5 treatments a week in 3 calendar days.

12.0 STUDY ASSESSMENTS

12.1 Overview

Study assessments were chosen to help understand the feasibility and effects of rTMS on individuals with stimulant use disorders. The assessments for this study balance the value of comprehensive data against feasibility and participant burden. Screening will evaluate full eligibility, including diagnosis of CUD and/or MUD and other psychiatric diagnoses. The study clinician must review and approve all safety and eligibility assessments to confirm participant eligibility prior to randomization. Excluding collection of study participant characteristics and locator information, the participant baseline data will include past alcohol and drug use including cocaine and methamphetamine using the Timeline Follow-Back (TLFB) method, use of other substances, quality of life, and other data chosen to evaluate the efficacy of rTMS in stimulant users (e.g., sleep). Table 5 provides a listing of administrative/data collection forms, and Table 6 includes the schedule for study specific assessments and procedures.

Table 5: Administrative Forms/Data Collection

	SC	RND	Double-Blind Treatment Phase								Post	FU	FU
Study Week	0	0	1	2	3	4	5	6	7	8	EOT	12	16
Pre-Screen Summary	X												
Randomization Enrollment Form	X												
Daily rTMS Treatment Log			X	X	X	X	X	X	X	X			
Visit Documentation			X	X	X	X	X	X	X	X	X	X	X
Protocol Deviation Form	-	-	-	-	-	-	-	-	-	-	-	-	-
End of Treatment Form											X		
Study Completion													X
Mental Health Assessment Follow-up	-	-	-	-	-	-	-	-	-	-	-	-	-
Serious Adverse Event Summary	-	-	-	-	-	-	-	-	-	-	-	-	-
Inventory Medication and Supplies	-	-	-	-	-	-	-	-	-	-	-	-	-
Actigraph Device Discontinuation			-	-	-	-	-	-	-	-	X		
EEG Completion (if available)			X			X							

- Completed as necessary

12.2 Administrative Forms

12.2.1 Pre-Screen Summary

This form provides the lead team with basic information for each potential participant pre-screened from each site.

12.2.2 Randomization Enrollment

The Randomization Enrollment form collects information regarding eligibility during the screening phase. Eligibility will be re-assessed prior to randomization. Only participants who continue to meet study eligibility criteria will be allowed to continue with the screening process and randomization.

12.2.3 Daily rTMS Treatment Log

This form is reported by study coordinator and captures treatment parameters for each rTMS treatment. This includes information such as current motor threshold, date of treatment, date of last motor threshold determination, duration of treatment, treatment location, coil-type, number of trains in treatment, and number of pulses in treatment.

12.2.4 Visit Documentation Form

This form documents visit attendance or non-visit attendance. This assessment has been recently developed to document visits that could occur out of window, offsite, or missed due to COVID-19. This is a visit-based form expected at most visits. If a visit is missed for any reason, this form will capture the reason a study visit was missed. Completing this form and indicating that the visit was not attended, will remove the requirement for all assessments scheduled for that visit. Active tracking and follow-up should be performed for all missed visits. The form also captures specific data collection settings if applicable (such as in clinic, offsite, or remote).

12.2.5 Protocol Deviation Form

This form should be entered into the electronic data capture system whenever a protocol deviation occurs. This form will document a description of the deviation, how it occurred, the corrective action taken to resolve the specific deviation, as well as a description of the plan implemented to prevent future occurrences of similar deviations. This form will also capture protocol deviations that were a result of COVID-19 specific restrictions.

12.2.6 End of Treatment Form

This form tracks the participant's status with regard to the study intervention. It will be completed at the end of treatment visit or at the end of the treatment visit window.

12.2.7 Study Completion Form

This form tracks the participant's status in the study. It is completed at the week 16 follow-up visit, or once the week 16 follow-up visit window lapses for participants who do not complete this final follow-up. If the participant withdraws consent, dies or is removed from the study per judgement of research staff, this form will be completed at the time of termination from the study. This form is used in data analyses to address variables such as treatment retention and completion. This form also provides a location for the site PI attestation of review of all study data.

12.2.8 Mental Health Follow-Up Assessment

This assessment must be completed if the participant endorses suicidal thoughts in the Concise Health Risk Tracking – Self Report (CHRT-SR) Suicidal Behavior Evaluation. The completion of the Mental Health Assessment form documents that a clinician has been notified. The site is required to have the participant evaluated by a qualified clinician in accordance with the site's specific SOP.

12.2.9 Serious Adverse Event Summary

This form will be completed for a given participant if they have a reportable serious adverse event and is intended to capture vital safety data for those events

12.2.10 Actigraph Device Discontinuation

This form will collect information on when the participant stopped using/wearing the actigraph device, as well as the reason for discontinuation of use.

12.2.11 EEG Completion

For sites equipped to conduct EEG assessments, this form documents whether the EEG was completed, and if not, why the EEG was not performed. The form is completed after randomization and again at week 4.

Table 6: Schedule of Assessments and Procedures

	SC	RND	Double-Blind Treatment Phase								Post	FU	FU
Study Week	0	0	1	2	3	4*	5	6	7	8*	EOT^	12	16
Informed Consent	X												
Locator Form and Updates	X	-	-	-	-	-	-	-	-	-	-	-	-
EMA Contact Form		X	-	-	-	-	-	-	-	-	-	-	-
PhenX Toolkit Core Tier 1#													
Demographics	X												
Treatment Status Form	X												
Quality of Life	X										X	X	X
Self-Report of HIV testing	X												
Tobacco Use History	X												
Alcohol and Other Substance Use	X												
Medical Assessments													
Physical Exam	X												
Medical and Psychiatric History	X												
Vital Signs	X		X			X					X	X	
Adverse Events	-	-	-	-	-	-	-	-	-	-	-	-	-
Prior/Concomitant Medications*	X	-	-	-	-	-	-	-	-	-	-	-	-
Penetration of Blind Assessment							X				X		X
Electroencephalogram (EEG) (if available)		X			X								
Psychological Assessments													
MINI 7.0.2	X												
Hospital Anxiety and Depression Scale (HADS)	X	X	X	X	X	X					X	X	X
Pittsburgh Sleep Quality Index	X					X					X		X
CHRT-SR Suicidal Behavior Evaluation*	X			X	X	X	X	X	X	X	X	X	X
CHRT-CR Suicidal Behavior Evaluation	-		-	-	-	-	-	-	-	-	-	-	-
Substance Use Self-Report													
TLFB*	X		X	X	X	X	X	X	X	X	X	X	X

	SC	RND	Double-Blind Treatment Phase								Post	FU	FU
Study Week	0	0	1	2	3	4*	5	6	7	8*	EOT^	12	16
Caffeine Intake Assessment	X		X	X	X	X	X	X	X	X			
DSM-5 Checklist	X												
Cannabis Use Assessment	X												
Fagerström Test for Nicotine Dependence [†]		X				X					X	X	X
Cue Craving Assessment [€]			X	X	X	X	X	X	X	X			
Other Assessments													
Protocol Satisfaction Form											X		
Daily Mobile Survey [∞]			X	X	X	X	X	X	X	X	X	X	X
Actigraphy			X	X	X	X	X	X	X	X			
Lab Testing													
Urine Drug Screen	X		X	X	X	X	X	X	X	X	X	X	X
Urine Pregnancy Test [‡]	X	X				X				X			

SC=Screening/Assessment, RND=Randomization, EOT=End of Treatment, FU=Follow-Up, [†] tobacco smokers only, [‡]females only, ^{*}required by NIDA/CCTN. Timepoints 1-8 represent weeks of treatment; ^{*}assessment will occur weekly during the 8-week treatment/sham phase, [€]assessment will occur after cue presentation and end of rTMS session at each visit during the treatment/sham phase; [∞]assessment will occur daily during the treatment/sham phase, and throughout the follow-up period. (-) indicates administration as appropriate. [^]EOT will also be completed for participants who withdraw early from the study. ^{*}If either weekly visits 4 or 8 are missed, assessments that are only completed at those visits should be performed at the next attended visit.

12.3 General Assessments

12.3.1 Locator Form

A locator form is used to obtain information to assist in finding participants during study participation. This form collects the participant's current address, email address, and phone numbers. In order to facilitate locating participants if direct contact efforts are unsuccessful, addresses and phone numbers of family/friends who may know how to reach the participant are collected. Social security number, driver's license number and other information will be collected to aid both in searches of public records (for locating participants in the above scenario) and issuing appropriate tax documents based on participant compensation. This information will be collected on paper at screening and will be updated at each visit or whenever the participant reports a change in locator information. No information from this form is used in data analyses.

12.3.2 EMA Contact Sheet

A system-based form will be used to collect participant's email address and mobile number. This information will be used to distribute daily mobile surveys assessing cocaine or methamphetamine related outcomes to participants, and will be updated by site staff if participants change service providers, mobile numbers and/or email addresses throughout the course of the study. In addition, participants will be able to unsubscribe or re-enroll to the mobile surveys during the course of the study, and site staff will also have the ability to unsubscribe or re-enroll participants to receive mobile surveys within the system.

12.3.3 Phen-X Toolkit Core Tier 1

The Substance Abuse and Addiction Collection of the Phen-X Toolkit (<http://www.phenxtoolkit.org/>) includes measures that are being adopted across NIDA-funded research. The Core Tier 1 collection includes measures for demographics (age, ethnicity, gender, race, educational attainment, employment status, marital status), BMI, and self-report of HIV test; substance use measures include age of onset, past 30-day quantity and frequency, lifetime use for alcohol, tobacco and other substances. Core Tier 1 assessments are completed at screening only.

12.3.4 Additional Demographics

A study-specific demographics form will collect information regarding gender identity and sexual orientation.

12.3.5 Protocol Satisfaction Survey

Participants will complete a Protocol Satisfaction Survey at the end of treatment visit. If the participant does not attend that visit, it should be completed at the next attended visit (either the week 12 or 16 post-randomization follow-up visit). This form will assess the acceptability of study procedures, time, compensation, treatment intervention and other aspects of their experience, including a free-response (qualitative) item regarding how the treatment/intervention made them feel.

12.3.6 Quality of Life

Participants will complete a standardized quality of life assessment used by the NIDA CTN from the CDC Behavioral Risk Factor Surveillance System (BRFSS), the Health Related Quality of Life (HRQOL-4) measure. This form assesses health-related quality of life in the past 30 days, and includes an overall self-reported rating of general health (from 'Poor' to 'Excellent'). This form is collected at screening, EOT, week 12, and week 16.

12.4 Medical Assessments

12.4.1 Physical Examination

A brief physical exam will be performed by the study Medical Clinician at the screening visit to assess whether individuals are medically stable for study inclusion. For staff/participant convenience, this may be done at Randomization as long as it is completed prior to randomization.

12.4.2 Medical and Psychiatric History

The study clinician obtains a medical and psychiatric history from the participant covering past and present health conditions to help determine eligibility and to provide baseline information. This is collected during screening. For staff/participant convenience, this may be done at Randomization as long as it is completed prior to randomization.

12.4.3 Vital Signs

Valid measures of height (at screening only) weight, blood pressure, and pulse will be collected at screening, initial treatment visit in week 1, initial treatment visit in week 4, initial treatment visit in week 8 and end of treatment.

12.5 Adverse Events (AEs), Serious Adverse Events (SAEs), and Unanticipated Adverse Device Effects (UADE)

12.5.1 AEs, SAEs and UADEs

At each visit the study staff assesses for AEs and SAEs by asking the study participant, "How have you been feeling since your last visit?" AEs and SAEs may also be spontaneously reported to study staff at any visit following consent. The Medical Clinician will review all AEs at least weekly. Any AE suggesting medical or psychiatric deterioration will be brought to the attention of a Medical Clinician immediately for further evaluation and management. Similarly, any SAE will be brought to the attention of the Medical Clinician immediately for further evaluation and reporting as required. Visits will emphasize overdose risk and risk-management; any reported overdose is recorded as an AE or SAE. AE and SAE reporting are according to the reporting definitions and procedures outlined in the protocol and in accordance with applicable regulatory requirements.

Device safety data will include the incidence of SAEs (e.g., worsening depression, suicidal ideation, suicide attempt, suicide, switching to hypomania/mania, seizure, death, and device malfunction resulting in patient or operator injury). In accordance with FDA recommendations, this protocol includes a suicide severity rating scale (CHRT) to assess both suicide intent and behavior. Incidence of common adverse events such as headache, application site pain will be collected, as well as discontinuation rate due to adverse events. Severity and duration of each AE will be determined. Data on each AE will include information about the intervention that was performed and whether the event was resolved. In addition, study staff will assess participants for signs of UADE, and will bring potential UADEs to the Medical Clinician for evaluation. Any UADE identified will be reported in accordance with applicable regulatory requirements (i.e., reported to the IRB for an abbreviated IDE as regulated under 21 CFR 812).

Any events that meet the definition of an AE and/or SAE are reported on the AE/SAE form set. Any spontaneous reporting of withdrawal symptoms by the participant are captured on AE form in the following situations: withdrawal symptoms reported at visits without scheduled specific structured questionnaires; and withdrawal symptoms not listed in the specific structured questionnaires reported at any visit.

12.5.2 Prior and Concomitant Medications

For safety purposes, all medications taken by the participant for the 30 days prior to screening, during screening, and during the active study will be documented on a Prior/Concomitant Medications assessment. All medications taken by the participant while in the study should ideally be pre-approved by the Medical Clinician.

12.5.3 Penetration of Blind Assessment

Participants and primary study personnel will be asked whether they think the participant is receiving rTMS or sham. This will be collected at the initial visit of treatment week 4, end of treatment, and final Follow-Up visit (week 16).

12.5.4 EEG Biomarker of Treatment Response

Electroencephalography (EEG) is a quick and well-tolerated procedure to measure the summed electric potential of the brain measured at the scalp. Resting-state EEG will be recorded (5 minutes resting eyes open, 5 minutes resting eyes closed) using a saline-based, high-density (≥ 64 channels) montage. At sites where EEG is available this procedure will be done prior to rTMS/sham treatment and again at approximately week 4. The week 4 EEG will only be obtained for those participants for whom the EEG was conducted at randomization.

12.6 Psychological Assessments

12.6.1 Mini International Neuropsychiatric Interview Plus

The MINI (Sheehan et al., 1998) is a semi-structured interview designed to ascertain a current, past, or lifetime history of the major Axis I psychiatric disorders in DSM-IV and ICD-10. Based on the original MINI, an expanded version (MINI 7.0.2) has been developed and validated for DSM-5. The MINI 7.0.2 will be administered (excluding the substance use section) by trained staff and used to evaluate for psychiatric disorders during the screening appointment. Equivocal diagnoses will be confirmed by the Medical Clinician.

12.6.2 Hospital Anxiety and Depression Scale (HADS)

The HADS (Zigmond & Snaith, 1983) is a brief, validated instrument that screens for both depression and anxiety (Bjelland et al., 2002). It will be administered at screening, once during weeks 4 and 8 of treatment, at the end of treatment assessment, and at each follow-up assessment.

12.6.3 The Pittsburgh Sleep Quality Index (PSQI)

The Pittsburgh Sleep Quality Index (PSQI; Buysse et al., 1989) will be used to complement standard AE assessment of sleep changes. The PSQI is a relatively brief, validated instrument that measures sleep quality. The PSQI is designed to be administered every 30 days and will be completed following the schedule outlined in the study timetable.

12.6.4 Concise Health Risk Tracking – Participant Rated Module (CHRT-SR) Suicidal Behavior Evaluation

The CHRT-SR (Trivedi et al., 2011) is a 16-item participant self-report assessment of suicidality and related thoughts and behaviors. The scale is designed to quickly and easily track suicidality in a manner consistent with the Columbia Classification Algorithm of Suicide Assessment (C-CASA) (Posner et al., 2007). The CHRT-SR will be assessed at screening, every week during the treatment phase, at the end-of-treatment assessment, and at the 12- and 16-week follow-up assessments. Responses on the measure will always be reviewed by research staff prior to visit

conclusion. Individuals who report a significant suicidal/homicidal risk, as indicated by a response of 2 or greater (Agree or Strongly Agree) on Items 14, 15 or 16 (the final 3 suicidal thoughts items) will be assessed by a qualified clinician before leaving the clinic (see the Concise Health Risk Tracking – Clinician Rated measure below).

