10.4.5 Clinical Deterioration “Rescue” Plan

A clinical deterioration “rescue” plan will be in place for participants who experience psychiatric or SUD deterioration during the study. Symptoms will be monitored closely throughout the trial to assess for deterioration (e.g., using the suicidality items on the Concise Health Risk Tracking questionnaire). Those who endorse suicidal thoughts or intent on the CHRT-SR will be further assessed on the CHRT-Clinician Rated assessment. Appropriate intervention will be arranged for any participant demonstrating gross clinical deterioration or suicide risk. The rescue measures will include referral for appropriate clinical intervention, including removal from the study and referral to SUD treatment should the participant demonstrate increasing substance use.

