12.6.5 Concise Health Risk Tracking – Clinician Rated Module (CHRT-CR)

The CHRT-CR will be performed by the Medical Clinician only if a participant answers any of questions 14-16 on the CHRT-SR as Agree or Strongly agree as described above. This assessment will also include, as needed, more comprehensive risk assessment/safety planning provisions, as well as potentially hospitalization, following site-specific hospitalization protocols.

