8.5 Suicide Risk

8.5.1 Self-Reported

The CHRT-SR (CHP) form is a self-reported assessment of suicidality and related thoughts and behaviors (Trivedi et al., 2011) assessed at screening, weekly during the treatment period, and at follow-up visits. Participants reporting suicide ideation/intent is defined as answering “Agree” or “Strongly Agree” on any of the Concise Health Risk Tracking – Participant Rated (CHRT-SR) questions 14, 15 or 16: “I have been having thoughts of killing myself”, “I have thoughts about how I might kill myself” or “I have a plan to kill myself.” The number and percentage of randomized participants with suicide ideation/intent will be summarized by presence or absence of current MDE assessed at baseline, study period, treatment arm, and overall.

A detailed listing for all visits for randomized participants who report suicide ideation/intent at any visit will be provided by treatment arm. The listing will include site, participant ID, date of randomization, presence or absence of current MDE assessed at baseline, visit, date of assessment, and responses to the suicide risk questions.

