xxxxx	xxxxxxxxxxxxxx	mm/dd/yyyy	mm/dd/yyyy	xxxxxxxxxx	Grade 1 – Mild Grade 2 – Moderate Grade 3 – Severe	None Decreased rTMS/sham "dose" Temporarily stopped rTMS/sham Permanently stopped rTMS/sham	Recovering/ resolving Recovered/ resolved Recovering/ resolved with sequelae Not recovered/ not resolved Fatal Unknown	mm/dd/yyyy	Congenital anomaly or birth defect Persistent or significant disability or incapacity Death Initial or prolonged hospitalization Life threatening Other serious event (Important Medical Event)	xxxxxxxxxx	xxxxxxxxxx

SAEs are highlighted in grey.

Table 69: Summary of CHRT – Participant Rated by Treatment Arm

Major Depressive Episode ¹	Number with suicide ideation/intent on CHRT-SR ^{2,3}	Treatment Arm		Total (N=XX)
		Sham (N=XX)	rTMS (N=XX)	
Absent	During screening	N (X.X%)	N (X.X%)	N (X.X%)
	During treatment period			
	During follow-up period			
Present	During screening			
	During treatment period			
	During follow-up period			
Overall	During screening			
	During treatment period			
	During follow-up period			

¹ Current Major Depressive Episode is assessed via the Mini International Neuropsychiatric Interview at baseline.

² Concise Health Risk Tracking-Participant Rated (CHRT-SR). Suicide ideation/intent on CHRT is defined as a response of "Agree" or "Strongly Agree" on any of CHRT-SR questions 14, 15 or 16: In the past week "I have been having thoughts of killing myself", "I have thoughts about how I might kill myself" or "I have a plan to kill myself".

³ Unique randomized participants with suicidal ideation/intent, at least once during the treatment and/or follow-up period. Denominator is the number randomized.

Listing 5: CHRT¹ Participant Rated by Treatment Arm								
Treatment Arm = Sham								
Site	Participant ID	Date of Randomization	Major Depressive Episode²	Visit	Date of Assessment	I have been having thoughts of killing myself	I have thoughts about how I might kill myself	I have a plan to kill myself
xxxxxxxxxx	xxxxxxxxxxxxxx	mm/dd/yyyy	Absent/ Present	Screening Week 1 A1 Week 1 A2 etc.	mm/dd/yyyy	Strongly Disagree Disagree Neither Agree nor Disagree/ Agree Strongly Agree	Strongly Disagree Disagree Neither Agree nor Disagree Agree Strongly Agree	Strongly Disagree Disagree Neither Agree nor Disagree Agree Strongly Agree

All visits are included for randomized participants who answered, 'Agree' or 'Strongly Agree'. Responses of 'Agree' are highlighted in orange and 'Strongly Agree' are highlighted in red.

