Concise Health Risk Tracking- Clinician Rated Module (CHRT- CR) will be performed by the Medical Clinician only if a participant endorses any of questions 14 -16 on the CHRT-SR as “Agree” or “Strongly agree”. Percentage within the time period is calculated as the number of unique randomized participants with the specified type of suicidal ideation/attempt at least once during the week prior to the visit where the assessment occurs, divided by the number of participants randomized.

¹ Current Major Depressive Episode is assessed via the Mini International Neuropsychiatric Interview at baseline.

Listing 6: CHRT ¹ Clinician Rated by Treatment Arm											
Treatment Arm = Sham											
Site	Participant ID	Date of Randomization	Major Depressive Episode ²	Visit	Date of Assessment	Suicidal Ideation					
						Passive	Active/ Non-specific	Active with Method	Active with Method and Intent	Active with Method, Intent and Plan	
xxxxxxxxxx	xxxxxxxxxx	mm/dd/yyyy	Absent/ Present	Screening Week 1 A1 Week 1 A2 etc.	mm/dd/yyyy	No/Yes	No/Yes	No/Yes	No/Yes	No/Yes	No/Yes

All visits are included for randomized participants who answered, 'Agree' or 'Strongly Agree' to any of the Concise Health Risk Tracking - Participant Rated (CHRT-SR) questions 14, 15 or 16: In the past week "I have been having thoughts of killing myself", "I have thoughts about how I might kill myself" or "I have a plan to kill myself".

¹ Concise Health Risk Tracking – Clinician Rated Module (CHRT-CR) form.

² Current Major Depressive Episode is assessed via the Mini International Neuropsychiatric Interview at baseline.

Listing 6: CHRT ¹ Clinician Rated by Treatment Arm											
Treatment Arm = rTMS											
Site	Participant ID	Date of Randomization	Major Depressive Episode ²	Visit	Date of Assessment	Suicidal Ideation					
						Passive	Active/ Non-specific	Active with Method	Active with Method and Intent	Active with Method, Intent and Plan	
xxxxxxxxxx	xxxxxxxxxx	mm/dd/yyyy	Absent/ Present	Screening Week 1 A1 Week 1 A2 etc.	mm/dd/yyyy	No/Yes	No/Yes	No/Yes	No/Yes	No/Yes	No/Yes

All visits are included for randomized participants who answered, 'Agree' or 'Strongly Agree' to any of the Concise Health Risk Tracking - Participant Rated (CHRT-SR) questions 14, 15 or 16: In the past week "I have been having thoughts of killing myself", "I have thoughts about how I might kill myself" or "I have a plan to kill myself".

¹ Concise Health Risk Tracking – Clinician Rated Module (CHRT-CR) form.

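### Protocol 12.6.4 equates a CHRT-SR response of 2 or more with Agree or Strongly Agree, which fits no conventional coding of the five-level scale shown in the SAP

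*Protocol*

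**What the plan says.** **Protocol 12.6.4 (CHRT-SR).** Significant risk is flagged "as indicated by a response of 2 or greater (Agree or Strongly Agree) on Items 14, 15 or 16". Participants flagged in this way "will be assessed by a qualified clinician before leaving the clinic", and the sentence refers forward to the clinician-rated measure (CHRT-CR).

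**Protocol 12.6.5 (CHRT-CR).** The Medical Clinician completes this form "only if a participant answers any of questions 14-16 on the CHRT-SR as Agree or Strongly agree as described above". No number is given.

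**Protocol 10.4.5 (rescue plan).** "Those who endorse suicidal thoughts or intent on the CHRT-SR will be further assessed on the CHRT-Clinician Rated assessment". There is no cut-off. Protocol 12.2.8 likewise ties the Mental Health Follow-Up Assessment to endorsement of suicidal thoughts, again without a cut-off.

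**SAP 8.5.1.** "Participants reporting suicide ideation/intent is defined as answering" *Agree* or *Strongly Agree* to question 14, 15 or 16. The footnote to Table 69 repeats this. The footnote to Table 70 says the CHRT-CR "will be performed by the Medical Clinician only if a participant endorses any of questions 14 -16 on the CHRT-SR as" one of the same two labels.

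**SAP 17.1.8, Listing 5.** The response options for the three items are shown as "Strongly Disagree Disagree Neither Agree nor Disagree/ Agree Strongly Agree". The slash is in the first item column only; the other two columns show the same five levels without it.

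Neither document attaches a numeric code to any of these levels.

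**The concern.** One sentence states the trigger twice, once as a number and once as two labels, and presents them as equivalent. If the scale has five levels and the usual codes, they are not equivalent. A person working from the number and a person working from the labels would then act on different responses.

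This is an operating safety threshold. The CHRT-SR is given at screening, weekly during treatment, at end of treatment and at both follow-up visits, in a population that includes people with a current major depressive episode. The trigger decides who is seen by a clinician at that visit. It also decides who gets a CHRT-CR, which is the source of SAP Table 70.

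The mismatch also sets 12.6.4 against 12.6.5. A response that meets the number but not the labels calls for assessment under 12.6.4, yet the restrictive wording of 12.6.5 rules out the CHRT-CR. A response that meets the labels but not the number has the opposite problem.

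**Working it through.** **Inputs**
- Numeric rule: response of at least 2 on item 14, 15 or 16 (Protocol 12.6.4).
- Label rule: *Agree* or *Strongly Agree* on any of those items (Protocol 12.6.4 and 12.6.5; SAP 8.5.1; footnotes to SAP Tables 69 and 70).
- Scale: five ordered levels with a neutral middle (SAP Listing 5).
- Codes: not given. Assumed to be consecutive integers rising with agreement, then varied.

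**General condition.** Let the lowest level, *Strongly Disagree*, have code a. Then *Neither* is a + 2 and *Agree* is a + 3. The numeric rule picks out exactly the top two levels only if *Neither* falls below 2 and *Agree* does not:

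a + 2 < 2 ≤ a + 3, that is, -1 ≤ a < 0.

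The only integer solution is a = -1, which is a scale coded -1 to 3.

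**Conventional codings**

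| Coding | Levels with code ≥ 2 | Against *Agree* or *Strongly Agree* | Cut-off that would reproduce the labels |
|---|---|---|---|
| 0 to 4 | *Neither*, *Agree*, *Strongly Agree* | adds one level | 3 |
| 1 to 5 | *Disagree*, *Neither*, *Agree*, *Strongly Agree* | adds two levels | 4 |
| -2 to +2 | *Strongly Agree* | leaves out one level | 1 |

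The last column only shows the size of the mismatch. It does not recommend a trigger.

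**Wider check.** Trying every integer start from -4 to 4, in rising and falling order, gives 9 × 2 = 18 codings. Exactly one matches, the rising -1 to 3 scale found above. A four-level scale without the neutral option, coded 0 to 3, would also match, because 2 and 3 would then be *Agree* and *Strongly Agree*. The SAP does not show that scale.

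**Consequence for the two Protocol sections**
- Coded 0 to 4: *Neither* meets the number in 12.6.4 but fails the label condition in 12.6.5.
- Coded 1 to 5: the same holds for *Disagree* and *Neither*.
- Coded -2 to +2: *Agree* meets the labels but fails the number.

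**Consequence for the SAP tables.** Table 69 counts participants by label, so no reading of the number changes its definition. Table 70 counts findings on the CHRT-CR over the number randomized. If a site acted on the number, forms could be added under the first two codings or omitted under the third.

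**The case against.** The strongest reply is that the sentence explains its own number. The labels follow it in parentheses, so no reader of 12.6.4 meets the number alone. Section 12.6.5 then restates the rule in labels and points back to 12.6.4. Every other place that gives a cut-off, in Protocol or SAP, uses the labels. On this view the numeral is a single clerical slip. It is also late to matter: SAP section 7.10 describes changes made after database lock, so new wording cannot alter what sites did.

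Much of this stands. It makes error less likely and limits the corrections needed. It does not remove the conflict, because the numeral is still part of an operative safety rule, and nothing in the documents says that the labels prevail.

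Three stronger readings are tempting, and the documents do not support them.
- A reader might infer that number and labels can never agree. The codes are not printed, and an unusual -1 to 3 coding would make them agree.
- A reader might infer that both suicidality tables are in doubt. Table 69 is defined by labels and is not affected.
- A reader might infer that sites, or an automatic form alert, worked from the number. The documents list the participant form (CHP) and the clinician form (CHC) but describe no alert, and nothing shows any site using codes.

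**Conclusion.** The inconsistency is real and should be corrected. Under each of the three conventional codings of the SAP's five-level scale, the numeric trigger in Protocol 12.6.4 differs from the label trigger by one or two levels: wider by one for 0 to 4, wider by two for 1 to 5, narrower by one for -2 to +2. At most one of these can apply, so they show a range and not a cumulative effect.

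The conclusion rests on two assumptions: that the items have the five levels shown in the Listing 5 shell, and that they carry a conventional code. The likely effect is limited. Table 69 stands as defined. Table 70 would change only if sites acted on the number despite the adjacent labels and the restriction in 12.6.5. The documents do not show whether any did.

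**What to change.** - Reconcile Protocol 12.6.4 with 12.6.5 so that one set of responses is named, either by stating the code attached to each label or by removing the numeral. Which set is right is for the sponsor's clinicians.
- Make the endorsement wording in Protocol 10.4.5 and 12.2.8 refer to that same set. If the label set is kept, SAP 8.5.1 and the table footnotes need no change.
- Check whether any site procedure or form logic used the number. In the locked data, compare each CHC form with the responses to items 14 to 16 on the CHP form from the same visit: look for CHC forms with neither label recorded, and for *Agree* responses with no CHC form. Such cases may have other causes, so they call for a query before any conclusion. If the number was used, say so with Table 70.

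The cost is a few words in the Protocol, or a clarifying note now that data collection is over, plus one cross-tabulation and a question to the sites. No analysis method changes.
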